CPAP	Continuous Positive Airway Pressure
CRO	Contract Research Organization
CRP	C-Reactive Protein
CSR	Clinical Study Report
Css	Concentration, steady state
CT	Computerized Tomography
CXR	Chest X-Rays
CYP	Cytochrome P450
DMC	Data Monitoring Committee
DMP	Data Management Plan
ECG	Electrocardiogram
ECMO	Extracorporeal Membrane Oxygenation
eCRF	electronic Case Record Form
EDC	Electronic Data Capture
eGFR	Estimated Glomerular Filtration Rate
FAS	Full Analysis Set
FDA	Food and Drug Administration
FIO ₂	Fraction of inspiration oxygen
GCP	Good Clinical Practice
HR	Heart Rate
ICAM-1	Intercellular Adhesion Molecule-1
GI	Gastrointestinal
ICF	Informed Consent Form
ICU	Intensive Care Unit
IEC	Independent Ethics Committee
IL	Interleukin
IMP	Investigational Medicinal Product
IMV	Invasive Mechanical Ventilation
IRB	Institutional Review Board
IRS	Interactive Response System
ITT	Intention to Treat
IUS	Intrauterine hormone-releasing system
IV	Intravenous
KM	Kaplan-Meier
LD50	Lethal Dose 50%
LDH	Lactate Dehydrogenase
LR	Legal Representative
LTAC	Long Term Acute Care
MAP	Mean Arterial Pressure
MedDRA	Medical Dictionary for Regulatory Activities
mg	Milligram (s)
ml	Milliliter (s)
mcg	Microgram (s)
ng	Nanogram (s)

NET	Neutrophils Extracellular Traps
NSAIDs	Non Steroidal Anti Inflammatory Drugs
OI	Oxygenation index
PaO ₂	Partial pressure of oxygen
PaCO ₂	Partial pressure of carbon dioxide
PAI-1	Plasminogen Activator Inhibitor-1
PCR	Polymerase Chain Reaction
PEEP	Positive End Expiratory Pressure
PI	Principal Investigator
PIP	Peak Inspiratory Pressure
pg	Picogram (s)
PK	Pharmacokinetic
PMN	Polymorphonuclear cell (s)
PP	Per Protocol
RAGE	Receptor for Advanced Glycation End products
RALE	Radiographic Assessment of Lung Edema
RR	Respiratory Rate
RT-PCR	Reverse Transcriptase-Polymerase Chain Reaction
SAE	Serious Adverse Event
SAF	Safety Analysis Set
SAP	Statistical Analysis Plan
SOFA	Sequential Organ Failure Assessment
SpO ₂	Peripheral Capillary Oxygen Saturation
SUSAR	Suspected Unexpected Serious Adverse Reaction
TEAE	Treatment Emergent Adverse Event
TESAE	Treatment Emergent Serious Adverse Event
TID	Three times a day
TNFr1	Tumor Necrosis Factor receptor 1
TV	Tidal Volume
ULN	Upper Limit of Normal
VFDs	Ventilatory-free days

1. STUDY SYNOPSIS

CLINICAL STUDY SYNOPSIS:	
Study Code	REP0122
Title of Study	Phase 2, proof-of-concept, randomized, double-blinded, placebo-controlled, multicenter study to assess efficacy and safety of reparixin as add-on therapy to standard of care in adult patients with Acute Respiratory Distress Syndrome (RESPIRATIO)
Short title	Reparixin in Acute Respiratory Distress Syndrome (ARDS)
IND/EudraCT No.	161827/2022-001612-25
Study Centres (Country)	US, Germany, Italy
Development Phase	Phase 2, proof-of concept study
Objectives	
1. To characterize the efficacy of reparixin in ameliorating lung injury and systemic inflammation and expediting clinical recovery and liberation from mechanical ventilation in adult patients with moderate to severe ARDS ($\text{PaO}_2/\text{FIO}_2$ ratio ≤ 200). Furthermore, to assess the effect of reparixin on systemic biomarkers linked to a hyper-inflammatory ARDS phenotype.
 
2. CCI CCI
 
3. To evaluate the safety of reparixin vs. placebo in patients enrolled in the study.

Design and Methodology	
Phase 2, proof-of-concept, randomized, double-blinded, placebo-controlled, multicenter study.
 
All patients will receive therapy in line with current standard-of-care as it pertains to ARDS management (protocolized ventilator management will be made available to all sites in accordance with currently accepted standard of care). Patients will be randomized (1:1) to either reparixin or placebo. Duration of treatment will be 14 days with the option to extend to 21 days if the patient is still intubated on Day 14.

Study procedures	
The study will consist of 4 study periods:
 
Screening
 
Randomization and Baseline assessments
 
Treatment (14 days, with the option of extension up to 21 days if the patient is still intubated on Day 14)
 
Follow-up (up to 28 days and hospital discharge if later than 28 days; and then up to day 60).
 
Screening: Potential study patients with confirmed ARDS will be identified from those hospitalized at the participating clinical sites for disease management. Screening will be performed in consented patients for assessment of eligibility and will include:
 
 • Demographic data, past medical history, allergies to medications, disease-specific clinical information • Concomitant medications • History of side effects related to prior use of Non-Steroidal Anti-Inflammatory Drugs (NSAIDs) such as gastrointestinal (GI) bleeding or other form of bleeding, peptic ulcer disease • Blood sampling for measurement of hematology/biochemistry (Safety Laboratory Tests) and derived renal [Estimated Glomerular Filtration rate (eGFR) evaluation by 2021 CKD-EPI] and hepatic function [ALT/AST and bilirubin determination] (unless already collected for clinical care) • Pregnancy test (urine test is acceptable) in women of childbearing

potential; positive urine test results will be confirmed with a serum pregnancy test

- 12-lead ECG performed using local equipment (unless already collected for clinical care)
- PaO₂ and FIO₂
- Chest imaging [either chest x-ray ([CXR](#)) or computerized tomography ([CT](#)) scan]

Randomization and Baseline assessments: Patients successfully completing the screening process and confirmed eligible for the study will be randomized to either reparixin or placebo within 24 hours and as soon as possible from screening assessment. They then will proceed to the following baseline assessments, before start of treatment (day 1):

- PaO₂, PaCO₂ and FIO₂
- Vital signs: respiratory rate ([RR](#)), heart rate ([HR](#)), mean arterial pressure ([MAP](#))
- Invasive mechanical ventilation ([IMV](#)) parameters [tidal volume ([TV](#)), positive end expiratory pressure ([PEEP](#)), mean airway pressure, plateau airway pressure)
- Use of neuromuscular blocking agents and inhaled vasodilators
- Prone positioning
- Vasoactive medications (drug and dose calculated in norepinephrine equivalents)
- Sequential organ failure assessment ([SOFA](#)) score
- Blood sampling for measurement of IL-6, IL-8, PAI-1, TNFr-1, ICAM-1, RAGE
- CXR (screening values, if any, will be considered if screening was within 24 hours)

Treatment and post-treatment hospital stay assessments:

After the baseline assessments have been completed, patients will start receiving the IMP.

The following data will be collected daily from day 1 until extubation:

- PaO₂, PaCO₂ and FIO₂
- Vital signs: RR, HR, MAP
- IMV parameters (TV, PEEP, mean airway pressure, plateau airway pressure)
- Use of neuromuscular blocking agents and inhaled vasodilators
- Prone positioning
- Transition to Extracorporeal membrane oxygenation ([ECMO](#))
- Vasoactive medications (drug and dose calculated in norepinephrine equivalents)
- SOFA score
- Number of attempts at weaning defined as continuous positive airway pressure ([CPAP](#)) trial (CPAP 5 cmH₂O plus PEEP 5 cmH₂O) of 2 hours duration

If an initial extubation is followed by reintubation, the above parameters will be collected daily for each subsequent re-intubation period.

At days 2(± 8 h), 3(± 8 h), 7 ± 1 and 14 ± 2 a CXR will be performed [CXR performed for routine clinical care in intensive care unit ([ICU](#)) patients will be accepted].

	
On days 3(± 8h), 7± 1, 14± 2 blood samples will be obtained for measurement of the following plasma biomarkers: IL-6, IL-8, PAI-1, TNFr-1, ICAM-1, RAGE
 
Between extubation and day 28 or hospital discharge (if it occurs before day 28) the following data will be collected every 48± 8 hours:
 
• Vital signs: RR, HR, MAP• PaO₂ (or SpO₂) and FIO₂• Type of oxygen supportive therapies used, if any• Need for reintubation (after initial extubation) 
CC1 CC1 CC1
 
At day 28 and at hospital discharge, the following data will be collected:
 
• PaO₂ (or SpO₂) and FIO₂• Type of oxygen supportive therapies used, if any• Duration of IMV• ICU length of stay• Need for reintubation (after initial extubation)• Hospital length of stay• Performance of tracheostomy• Transfer to long term acute care (LTAC) facility 
Safety: The following safety assessments will be performed on day 3(± 8h), 7± 1, 14± 2, 21± 2 (if reparixin is still administered on day 21) and at day 28± 2 and hospital discharge
 
• Safety Laboratory Tests (Hematology/biochemistry)• Estimated Glomerular Filtration rate (eGFR) evaluation• Hepatic function evaluation (ALT/AST and bilirubin)• 12 lead ECG and rhythm analysis 
Post-hospital discharge follow-up: On day-60, the patients will be contacted by phone for evaluation of vital status, AEs.

Number of patients	60 evaluable patients. Assuming that 10% of enrolled patients will not be evaluable for primary analysis, approximately 66 patients will be enrolled

Diagnosis and Main Criteria for Inclusion/Exclusion	
Inclusion criteria
 
1. Signed Informed Consent, according to local guidelines and regulations.2. Male and female adults (≥ 18 years old)3. Mechanically ventilated (invasive) patients with $\text{PaO}_2/\text{FIO}_2$ ratio ≤ 200 in the presence of PEEP of ≥ 5 cm H₂O.4. Respiratory failure not fully explained by cardiac failure or fluid overload (if acute Congestive Heart Failure exacerbation is identified as part of the clinical picture, this should be addressed effectively and as soon as possible before the patient can be enrolled).5. Bilateral radiologic opacities consistent with pulmonary edema on the frontal chest x-ray (CXR) radiograph, or bilateral ground glass opacities on a chest CT scan.6. ≤ 48 hours from fulfilling above ARDS criteria (if a patient is transferred from a non-participating hospital to a participating site, a 12-hour period beyond the 48 hours is allowed)7. Females of child-bearing potential who are sexually active must be willing not to get pregnant within 30 days after the last Investigational Medicinal Product (IMP) dose and must agree to at least one of the following reliable methods of contraception:
• Hormonal contraception, systemic, implantable, transdermal, or injectable contraceptives from at least 2 months before the screening visit until 30 days after the last IMP dose;• A sterile sexual partner;• Abstinence.For patients unable to personally consent to the above, due to complications of acute illness and/or its treatment, assurances for the above must be given by LR and reiterated by the patient when/if she is able to do so. 
Female participants of non-child-bearing potential or in post-menopausal status for at least 1 year will be admitted. For all female subjects with child-bearing potential, pregnancy test results must be negative before first drug intake.

---	--

	Exclusion criteria
	
1. Moderate-Severe chronic hepatic disease (as verified by a previously known Child-Pugh score ≥ 7). If baseline Child-Pugh score is not known, it should not be calculated while the patient is acutely ill. In that case, the patient is excluded on the basis of: ALT/AST $\geq 3 \times$ ULN and total bilirubin $> 2 \times$ ULN or ALT/AST $\geq 5 \times$ ULN.2. Severe chronic renal dysfunction: eGFR (2021 CKD-EPI) $< 30 \text{ mL/min}/1.73\text{m}^2$. If baseline (chronic) renal function is not known, the patient is only excluded if in need of acute renal replacement therapy (currently on RRT or to be imminently placed on RRT).3. Participation in another interventional clinical trial.4. Patients that are clinically determined to have a high likelihood of death within the next 24 hours based on PI's estimation.5. Currently receiving ECMO or high frequency oscillatory ventilation.6. Anticipated extubation within 24 hours of screening. (In such cases, re-screening is allowed if the patient is within the enrollment window).7. Evidence of GI dysmotility as demonstrated by presence of all the following: persistent gastric distention and enteral feeding intolerance and persistent gastric residuals $> 500 \text{ ml}$.8. Anticipated transfer to a hospital not participating in the trial within 72 hours of screening.9. Decision to withhold or withdraw life-sustaining treatment (patients may still be eligible however if they are committed to full support except cardiopulmonary resuscitation if cardiac arrest occurs).10. History of:
a) Documented allergy/hypersensitivity to sulfonamides, ibuprofen and other COX-1 and 2 inhibitors, and to the study product and/or its excipients.b) Lactase deficiency, galactosemia or glucose-galactose malabsorption.c) History of peptic ulcer, GI bleeding or perforation due to previous NSAID therapy.11. Active bleeding (excluding menses) from an uncontrolled site that cannot be definitively resolved prior to enrollment.12. Pregnant or lactating women.13. Women of childbearing potential and fertile men who do not agree to use at least one primary form of contraception during the study and up to 30 days after the last IMP dose. 
For patients unable to personally consent to above due to complications of acute illness and/or its treatment, assurances for the above must be given by LR and reiterated by the patient when/if he/she is able to do so.

Test Product, Dosage and Mode of Administration	Reparixin 600 mg tablets, administered crushed through nasogastric tube at the dose of 1200 mg TID (2 tablets TID) as add-on to the standard of care. After extubation and if the patient can swallow, reparixin may be administered orally
Duration of Treatment	14 days with the option to continue up to 21 days, if the patient is still intubated on Day 14
Reference product, Dosage and Mode of Administration	Placebo tablets. Administered crushed through nasogastric tube with the same schedule as reparixin as add-on to the standard of care. After extubation and if the patient can swallow placebo may be administered orally
Primary efficacy endpoints	
 - Change in oxygenation index (OI) from baseline to day 7 of treatment. The OI is defined as: % mean airway pressure x $\text{FIO}_2/\text{PaO}_2$ - Ventilator free days (VFD) at day 28
Secondary endpoints	
 - Change in OI from baseline to day 4 - Acute lung injury score [composite of $\text{PaO}_2/\text{FIO}_2$ ratio, PEEP, lung compliance (plateau airway pressure minus PEEP/TV) and extent of pulmonary infiltrates] at 2, 3, 7, 14 days (if still intubated) - SOFA scores at 2, 3, 7, 14 days (if still intubated) - Ventilatory ratio (product of minute ventilation and PaCO_2) at 2, 3, 7, 14 days (if still intubated) - Incidence of ECMO by day 14 - Use of vasoactive medications by day 14 - CXR assessment of pulmonary edema by “radiographic assessment of lung edema” (RALE) score at 2, 3, 7, 14 days - Percentage of patients achieving pressure support ventilation equal to 5 cm H₂O with PEEP equal to 5 cm H₂O for 2 hours (measure of weaning) by day 28 and at hospital discharge - ICU-free days by day 28 and hospital discharge - Hospital-free days by day 28 and hospital discharge - Incidence of tracheostomies by day 28 and hospital discharge - Incidence of transfer to long term acute care (LTAC) facility by day 28 and hospital discharge - All-cause mortality by day 28 - Hospital discharge by day 28 - All-cause mortality by day 60 - Change from baseline to day 3, 7 and day 14 in plasma levels of IL-6, IL-8, PAI-1, TNFr-1, ICAM-1 RAGE
CC1	CC1 
Safety endpoints	
 • Incidence of Treatment Emergent AEs (TEAEs) and SAEs (TESAEs) from the beginning of study treatment to up to the end of study participation. • Hematology/biochemistry values change from screening to day 3($\pm 8h$), 7± 1, 14± 2, 21± 2 (if still receiving reparixin), 28± 2 and hospital discharge. • eGFR, absolute value and change from screening to day 3($\pm 8h$), 7± 1, 14± 2, 21± 2 (if still receiving reparixin), 28± 2 and hospital discharge. • Hepatic function (ALT/AST, total/direct bilirubin), absolute

	
values and change from screening to day 3($\pm 8h$), 7± 1, 14± 2, 21± 2 (if still receiving reparixin), 28± 2 and hospital discharge.
 
• ECG/rhythm analysis changes from screening to day 3$\pm 8h$, 7± 1, 14± 2, 21± 2 (if still receiving reparixin), 28± 2 and hospital discharge.• Incidence of secondary infections by day 28± 2 or hospital discharge.
Statistical Methods	
A sample size of 60 evaluable subjects is considered adequate for descriptively assessing the difference between groups in primary endpoints, i.e. change from baseline in OI at day 7 and VFD at day 28. Assuming equal size groups (1:1), the given sample size will provide a reasonable precision in the estimation of group differences in primary endpoints to an expected margin of error for a 95% one-sided confidence interval of at most 46.5% the standard deviation, whatever it is. Consequently, assuming a standard deviation of 11.5 points for OI and of 8 days for VFD (based on literature), the 95% one-sided confidence intervals for the differences between groups will have a width of 5.35 points and 3.75 days, respectively.
 
Assuming that 10% of enrolled patients will not be evaluable for primary analysis, the total number of patients to be enrolled will be approximately 66.
 
Appropriate descriptive statistics will be produced by treatment arms according to the nature of the variable. For continuous data, number of observations, mean, standard deviation, median, range (minimum and maximum) and 95% confidence intervals will be presented. For categorical data, frequency distributions and percentages with 95% confidence intervals (Wilson method) per category will be presented. The Safety and the Full Analysis Set (FAS) populations will consist of all patients who will be randomized and received at least one dose of the investigational product. Safety population will be analyzed according to the actual treatment received; FAS population will be analyzed according to the Intention To Treat principle, i.e. by treatment allocation.
 
All secondary endpoints will be analyzed at each available time point by means of summary statistics and by appropriate parametric or non-parametric tests depending on the nature of the variable and its distribution. All analyses will be descriptive in nature.
 
TEAEs and TESAEs will be presented in terms of the number and incidence of TEAEs and TESAEs. Other safety parameters will be summarized by treatment at each available time point by means of descriptive statistics.
 
The Study Statistical Analysis Plan with more technical and detailed elaboration of the principal features of statistical analyses will be finalized before database lock. Any deviation from the original statistical plan will be described in the Clinical Study Report.

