2. SCHEDULE OF EVALUATION

The grid below summarizes the study schedule of the trial. For all measurements, the actual date and time of assessment, including date of sampling, will be recorded in the Source Document and/or eCRFs. Timeframe for each assessment is also shown in the grid below.

Days (windows)	Screening (day-1 or 1)	Randomization and baseline assessments ¹	Day 1	Day 2 (±8h)	Day 3 (±8h)	Day7 (±1)	Day 14 (±2)	End of Treatment ²	Extubation to Hospital Discharge (every 48h±8h)	Day 28 (±2) and Hospital Discharge ¹⁹	Day 60
ELIGIBILITY											
Informed consent signed	X										
Demo-graphics, Medical History, Disease-Specific Information, allergies	X										
Pregnancy test ²	X										
STUDY INTERVENTION											
Randomization		X									
IMP administration ³			Daily through day 14 with the option to extend to day 21								
STUDY PROCEDURES											
Vital signs (RR, HR, MAP)			Daily through extubation				X				
PaO ₂ (or SaO ₂), FIO ₂	X		Daily through extubation				X	X			
PaCO ₂			Daily through extubation								
Mechanical ventilation parameters ⁴			Daily through extubation								
SOFA score			Daily through extubation								
Neuromuscular blocking agents, inhaled vasodilators ⁵			Daily through extubation								
Prone positioning ⁶			Daily through extubation								
Vasoactive medications ⁷			Daily through extubation								
ECMO ⁸			Daily through extubation								
CPAP attempts ⁹			Daily through extubation								
Chest imaging ¹⁰	X	X	X	X	X	X					
Biomarkers ¹¹		X		X	X	X					
Reintubation ¹²									X		
Other clinical events ¹³									X		
Follow up ¹⁴										X	
SAFETY TESTS											
Adverse events	↔										
Concomitant medications	↔										
Safety hematology and	X				X	X	X	X		X	

Days (windows)	Screening (day-1 or 1)	Randomization and baseline assessments ¹	Day 1	Day 2 (-8h)	Day 3 (-8h)	Day 7 (±1)	Day 14 (±2)	End of Treatment ²¹	Extubation to Hospital Discharge (every 48h±8h)	Day 28 (±2) and Hospital Discharge ¹⁹	Day 60
biochemistry ¹⁵											
eGFR ¹⁶	X			X	X	X	X			X	
Hepatic function ¹⁷	X			X	X	X	X				
ECG	X			X	X	X	X				X ²¹
CCI											

1. Baseline and initiation of IMP (day1) may coincide
2. In females of childbearing potential, only date will be required
3. Study product will be administered every 8 hours (q8h) for 14 days, and optionally up to 21 days
4. Mode of ventilation, TV, mean airway pressure, plateau airway pressure, PEEP
5. Use or not of neuromuscular blocking medications and/or inhaled vasodilators

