5.3.2. Criteria for permanent discontinuation of the IMP

The IMP must be discontinued in the case:

- Upon initiation of renal replacement therapy;
- Upon increase of ALT and/or AST to ≥ 3 x ULN and total bilirubin > 2 x ULN or upon increase of ALT and/or AST to ≥ 5 x ULN
- The patient is discharged home;
- Withdrawal of informed consent by the patient or his/her legal representative (in this case, the patient / representative will be asked whether they consent to usage of the data already collected in the study; if not, the data will be deleted);
- Pregnancy occurs;
- Development of Serious AE probably or possibly related to IMP, as per PI's judgment;
- Inadvertent missing of 3 or more consecutive doses of the IMP;
- Inability to resolve within 24 hours any medical condition/event that led to temporary withholding of the IMP (see also 5.3.3.);
- Recurrence of AE probably or possibly related to IMP upon re-introduction of the IMP.

Occurrence of renal or hepatic dysfunction will be monitored as part of the biochemistry data set through safety laboratory tests obtained at day 3 ± 8 h, 7 ± 1 , 14 ± 2 , and 21 (if the IMP is meant to be administered up to 21 days). The other criteria that qualify the patient to treatment discontinuation will be monitored daily.

If the IMP administration is prematurely discontinued, the primary reason for discontinuation must be recorded in the eCRF. Patients who discontinue the treatment with the IMP will NOT be withdrawn from the study by default and will be asked to complete safety and efficacy observations as per the protocol unless they withdraw their consent.

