7.2. SAFETY ENDPOINTS

- Hematology (RBC, hematocrit, hemoglobin, WBC, neutrophils and lymphocytes absolute count, platelets count) and biochemistry (sodium, potassium, chloride, calcium, glucose, creatinine, eGFR albumin, AST, ALT, total and direct bilirubin). Change from screening to day 3 ± 8 h, 7 ± 1 , 14 ± 2 , 21 ± 2 (if still receiving reparixin, or end of treatment), 28 ± 2 and at hospital discharge
- eGFR, absolute value and change from screening to day 3 ± 8 h, 7 ± 1 , 14 ± 2 , 21 ± 2 (if still receiving reparixin, or end of treatment), 28 ± 2 and hospital discharge
- ECG. Change from screening to day 3 ± 8 h, 7 ± 1 , 14 ± 2 , 21 ± 2 (if still receiving reparixin, or end of treatment), 28 ± 2 and at hospital discharge
- Incidence of secondary infections defined as new (occurring after the first IMP intake) infection in a previously known to be sterile site, including blood, body fluid or tissue, or new pathogen isolated from cultures of biological samples known to be previously infected by day 28 ± 2
- Incidence of TEAEs and TESAEs from the beginning of IMP administration up to the end of study participation

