Day 3	1 st IMP intake Date/Time + 36h	1 st IMP intake Date/Time + 59h and 59 min	48h
Day 4	1 st IMP intake Date/Time + 60h	1 st IMP intake Date/Time + 83h and 59 min	72h
Day 5	1 st IMP intake Date/Time + 84h	1 st IMP intake Date/Time + 107h and 59 min	96h
Day 6	1 st IMP intake Date/Time + 108h	1 st IMP intake Date/Time + 131h and 59 min	120h
Day 7	1 st IMP intake Date/Time + 132h	1 st IMP intake Date/Time + 155h and 59 min	144h
Day 8	1 st IMP intake Date/Time + 156h	1 st IMP intake Date/Time + 179h and 59 min	168h
Day 9	1 st IMP intake Date/Time + 180h	1 st IMP intake Date/Time +203h and 59 min	192h
Day 10	1 st IMP intake Date/Time + 204h	1 st IMP intake Date/Time + 227h and 59 min	216h
Day 11	1 st IMP intake Date/Time + 228h	1 st IMP intake Date/Time + 251h and 59 min	240h
Day 12	1 st IMP intake Date/Time + 252h	1 st IMP intake Date/Time + 275h and 59 min	264h
Day 13	1 st IMP intake Date/Time + 276h	1 st IMP intake Date/Time + 299h and 59 min	288h

Standard/Forms/Template				
Title		Statistical Analysis Plan Template		
Code		Version	Effective Date	Page
PPD		01	29 Aug 2022	16 of 78

Day 14	1 st IMP intake Date/Time + 300h	1 st IMP intake Date/Time + 323h and 59 min	312h
--------	---	--	------

Differently from what it was reported in the study protocol, the window used for each day is +/- 12 hours to let each assessment to be unequivocally classified in a given day (not possible by using the time window +/- 8h).

With the exception of Day 1, which covers 12 hours (11 h and 58 minutes), all the other days cover 24 hours (23h and 59 min).

For each endpoint described in section 3.5.1 and 3.5.2, it will be specified whether the study Day will be defined on the basis of Date or Date/time. Section 11.1.1 provides further details with regards to variables derivations based on date or date/time.

Please refer to Table 1: Study Flow Chart for full details on the schedule of suggested assessments.

Notes:

- Study Days will be derived using the algorithms defined above.
- Analysis based on visits (Chest Imaging, labs, ECG ...) will use the assessments collected at that visit, regardless of the study days.

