3.2.3 Visit re-mapping

For the endpoints that use nominal visit, a visit re-mapping will be implemented.

In case data are missing at Day 2, Day 3, Day 7, Day 14, Day 28, and Day 60 analysis visit, data collected at End of treatment or Hospital discharge will be remapped as follows:

- if the date of collection is within the analysis timepoint window , it will be remapped to the missing scheduled timepoint (example: End of Treatment happens at day 13 of study and there is no data collected at visit Day 14 for that subject, then the data collected in the End of Treatment moment will be remapped to Day 14 and it will be used in the analysis for that timepoint).
- In case both "End of Treatment" and "Hospital Discharge" visits can be remapped to the same missing scheduled timepoint, the record closer to the nominal visit date will be remapped (e.g.: "Day 14" is missing, but "EOT" happened on day 14 and hospital discharge on day 15, both visits fit within the window of "Day 14" but only "EOT" will be remapped, as it's the closest one).
- In case both "End of Treatment" and "Hospital Discharge" visits can be remapped to the same missing scheduled timepoint, and are both at the same distance from the nominal visit, the one that occurs first, e.g. the EOT visit, will be remapped.

End of Treatment and Hospital Discharge will also be analyzed "as such", irrespective of whether they were also remapped to another study visit.

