8.2 Clinical laboratory evaluation

Analysis of clinical laboratories data will be performed by treatment for Hematology and Biochemistry (including eGFR) tests. In case of different units of measure considered for the same laboratory

Standard/Forms/Template				
Title		Statistical Analysis Plan Template		
Code		Version	Effective Date	Page
PPD		01	29 Aug 2022	53 of 78

parameter, all values will be converted into Standard International units (if applicable) or to the same unit. Even if laboratory are collected at screening and the protocol mention changes from screening, baseline and changes from baseline will be provided: this means that, if for some reason the screening assessment is done after treatment start date (by mistake or any reason), the value will not be considered in the analysis, since the value will not be flagged as "Baseline" (as defined in section 3.2.2). Subsequent timepoints are Day 3, Day 7, Day 14, Day 21, end of treatment, Day 28 and hospital discharge.

The following summaries will be provided:

- A summary table showing for all laboratory tests the values and changes from baseline to each subsequent visit.
- A summary table showing for all laboratory tests the frequency of the investigator's interpretation at each available visit.
- Shift tables presenting the number and the percentage of patients in each bivariate category (baseline versus each post-baseline visit) with regards to investigator's interpretation.

The following graphical representations will be provided for all laboratory parameters:

- Spaghetti plot of individuals' observed data and change from baseline (with x-axis marked by days relative to start of actual treatment);
- Boxplot for values and changes from baseline by actual treatment at each timepoint.

Listings showing hematology results, biochemistry results, abnormal clinically significant hematology results and abnormal clinically significant biochemistry results will be provided.

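### Day 21 is a stated safety time point for laboratory tests and ECG, but SAP 3.2.3 leaves it off the visit re-mapping list, so an End of Treatment record dated Day 19-23 cannot fill a missing Day 21

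*Protocol*

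**What the plan says.** **Day 21 as a safety time point.** The protocol synopsis (Safety) and Protocol 6.1.3 schedule laboratory tests, eGFR, hepatic function and ECG at Day 21±2 for patients still on treatment; the synopsis condition reads "if reparixin is still administered on day 21) and at day 28". Protocol 5.3.2 monitors renal and hepatic function at Days 3, 7, 14 "and 21 (if the IMP is meant to be administered up to 21 days". Protocol 7.2 words the condition as "if still receiving reparixin, or end of treatment".

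**Flow chart.** The grid in Protocol section 2, repeated as SAP Table 1, goes from Day 14 straight to "End of Treatment", where the safety tests are marked. Day 21 appears in the body of the grid only in the dosing row: "Daily through day 14 with the option to extend to day 21".

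**SAP.** Section 3.6 tags the Day 21 laboratory, eGFR, hepatic and ECG endpoints as by visit. Section 8.2 says "Subsequent timepoints are Day 3, Day 7, Day 14, Day 21, end of treatment, Day 28 and hospital discharge", and 8.4 likewise names both Day 21 and end of treatment for ECG. The notes to 3.2.1 say that visit-based analyses "will use the assessments collected at that visit, regardless of the study days". Section 3.2.3 then sets the fallback. It begins "In case data are missing at Day 2, Day 3, Day 7, Day 14, Day 28, and Day 60 analysis visit" and moves an End of Treatment or Hospital Discharge record to the missing visit if its date lies in that visit's window. Those two visits are also reported in their own right.

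**The concern.** For laboratory tests and ECG, the nominal visit label decides which row a value enters. The only route from End of Treatment to a day-specific row is the list in 3.2.3, and Day 21 is not on it. Yet Day 21 is the safety time point most likely to coincide with End of Treatment, because an extended course ends there. A sample taken once and entered under End of Treatment would not count as Day 21.

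Patients treated for 21 days have the longest exposure. Their liver, kidney and QTc values at the end of that exposure are what a Day 21 row is meant to show. If those values sit only under End of Treatment, they are tabulated together with values from patients who stopped at Day 14 or earlier, and the stated Day 21 change is summarised on whichever patients happen to have a record under that label.

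**Working it through.** There is no planned figure to reproduce. The check is to apply the rule in SAP 3.2.3 day by day.

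**Inputs**
- Re-mapping targets (SAP 3.2.3): Days 2, 3, 7, 14, 28, 60.
- Windows (flow chart and SAP 3.6): Day 14±2 = Days 12-16; Day 21±2 = Days 19-23; Day 28±2 = Days 26-30.
- Rule: a record dated d can fill a missing visit k if k is on the list and d lies in the window of k.

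**When a full extended course ends.** Three doses a day for 21 days is 3 × 21 = 63 doses. At 8-hour intervals the last is given 62 × 8 = 496 h after the first, and 496 / 24 = 20.7 days. That is study Day 21 or 22, depending on the clock time of the first dose. An End of Treatment visit at that point falls inside the Day 21±2 window.

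**Where an End of Treatment record can go**

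| Date of record | As written | With Day 21±2 added |
|---|---|---|
| Days 12-16 | Day 14 | Day 14 |
| Days 17-18 | none | none |
| Days 19-23 | none | Day 21 |
| Days 24-25 | none | none |
| Days 26-30 | Day 28 | Day 28 |

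As written, every date from Day 17 to Day 25 has no target, which includes the whole Day 21 window. Adding Day 21 creates no overlap with Day 14 or Day 28.

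**Comparison with the SAP's own example.** Section 3.2.3 illustrates the rule with End of Treatment on Day 13 and no Day 14 data; the record is moved to Day 14. End of Treatment on Day 21 with no Day 21 data is the same case, but there the record stays where it is.

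**Vital signs.** SAP 3.6 assigns these by date and time. By the rule in 3.2.1, Day 21 has its midpoint at (21 − 1) × 24 = 480 h and runs from 468 h to 491 h 59 min after first intake. Vital signs do not use the re-mapping list and are unaffected.

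**Number of patients.** The documents do not say how many patients will be extended. Purely as an illustration, if 20% to 35% of 66 were treated to about Day 21, that would be 0.20 × 66 = 13 to 0.35 × 66 = 23 patients. This is the number eligible for a Day 21 value under that assumption, not the number who would lack one.

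**The case against.** The strongest reply is that the eCRF may have its own Day 21 visit. SAP 3.6, 8.2 and 8.4 treat Day 21 and end of treatment as separate time points, which fits that. If the visit exists and is completed, the Day 21 rows are populated and the fallback is rarely needed. The grid is described as a summary, and some of its footnotes are blacked out, so a note explaining the End of Treatment column may exist. Protocol 7.2 can be read as making end of treatment an alternative to Day 21, but the synopsis and SAP 3.6 do not carry that wording. Since Day 21 is conditional, its omission could even be deliberate.

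Much of this stands. A reader might infer that the Day 21 tables will be empty. The documents do not show that, because the eCRF is not among them. A reader might also infer that effects of long exposure cannot be compared between arms. That goes too far: SAP 8.2 and 8.4 plan plots of individual values and changes by day from start of treatment, together with listings, and End of Treatment keeps its own row.

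What the reply does not remove is the unequal treatment. Days 2, 3, 7, 14, 28 and 60 are scheduled visits too, and the SAP still gives them a fallback when data are missing. A separate Day 21 page would make the gap smaller but would not close it.

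**Conclusion.** The gap is real and small. As the SAP stands, an End of Treatment laboratory or ECG record dated Day 19-23 cannot fill a missing Day 21. The Day 21 rows for laboratory tests, eGFR, hepatic function and ECG may therefore be incomplete. They would be empty only if the eCRF has no separate Day 21 visit, which the documents do not settle. For any patient affected, the end-of-exposure value would be tabulated only under End of Treatment, pooled with 14-day completers and early stoppers.

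No data are lost, vital signs are outside the problem, and the primary endpoints and sample size are unchanged. The number of patients affected cannot be derived from the documents. This is a free improvement of low impact, confined to descriptive safety reporting. It assumes that the windows for re-mapping are those of the flow chart and SAP 3.6.

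**What to change.** 1. Add Day 21 (Days 19-23) to the re-mapping list in SAP 3.2.3 for laboratory tests and ECG.
2. Limit it to patients who meet the protocol's Day 21 condition of still receiving treatment, put into operation as last IMP intake on Days 19-23, in both arms. Without this limit, a patient who stopped on Day 16 and was discharged on Day 20 would put an off-drug value into a row meant for patients still on treatment. With it, a discharge value could still follow the last dose by up to 23 − 19 = 4 days, so it is tidier to let the End of Treatment record take precedence over discharge at Day 21.
3. Keep the separate End of Treatment row as planned.
4. Reconcile the flow chart, Protocol 7.2 and SAP 3.6, 8.2 and 8.4 on whether Day 21 is its own visit or is served by End of Treatment for extended courses.

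The cost is one list entry with one condition, reuse of the existing re-mapping program, and a clarifying sentence. No new data are needed.
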